However, the ideal blood glucose range for maintaining our patients is still a subject of debate. Despite knowing that hyperglycemia is harmful, its treatment carries a high risk of hypoglycemia. Severe hypoglycemia (glucose <40 mg/dL) increases the risk of death from any cause in critically ill patients by more than threefold (6). The incidence of hypoglycemia in critically ill patients varies widely depending on the patient type and the protocol used for hyperglycemia control, but it is generally estimated that between 3% and 20% of critically ill patients may experience severe hypoglycemia during their hospitalization (7). On the other hand, hypoglycemia can be easily prevented or treated in hospitalized patients through the infusion of glucose solutions if correctly identified (8).

In recent years, the use of continuous subcutaneous glucose monitoring (CGM) sensors has revolutionized clinical practice in non-hospitalized diabetic patients (9). Subcutaneous glucose is directly related to capillary and arterial blood glucose (10), so changes in blood glucose concentration are transmitted to subcutaneous tissue within the next 5 to 10 minutes (11). CGM in critically ill patients has been shown to significantly reduce the incidence of hypoglycemia, mortality, and glycemic variability compared to standard practice (12).

Given the current evidence, a guide for the use of CGM sensors in critically ill patients undergoing insulin treatment has been developed in the Intensive Care Unit (ICU) of HLA Moncloa University Hospital. The main objective of this guide is to attempt to reduce episodes of severe hypoglycemia in these patients. The guide has been in use since May 2023 (ANNEX 1).

The primary utility of these sensors in critically ill patients lies in detecting patients at risk of experiencing hypoglycemia, which the investigators could consider as potential hypoglycemic events. However, to the best of our knowledge, there is currently no unified clinical practice regarding the use of these devices in critically ill patients. It is not possible to find clinical practice guidelines or recommendations for the thresholds for detecting potential hypoglycemic events or studies describing the characteristics of these events.

Therefore, this study aims to determine the cumulative incidence over the admission period and the incidence rate of potential hypoglycemic events (defined as subcutaneous glucose <80 mg/dL detected by CGM) occurring in patients admitted to the ICU at HLA Moncloa Hospital during a four-year follow-up. Additionally, it aims to describe the occurred hypoglycemic events, the type of patients using the CGM sensor, and the actions derived from the detection of potential hypoglycemic events.

Hypothesis and Objectives:

Hypothesis: It is expected that the risk of potential hypoglycemia in critically ill patients undergoing insulin treatment is 20% (7), and that measures will be taken in all patients with potential hypoglycemia to verify and, if necessary, prevent actual hypoglycemia.

Objectives:

Primary Objective:

- Determine the cumulative incidence or risk of potential hypoglycemia during ICU admission (cases of potential hypoglycemia/number of patients x 100) and the incidence rate (cases of potential hypoglycemia/1000 x patient x hour) in critically ill patients undergoing insulin treatment using CGM sensors. Potential hypoglycemia will be considered when the CGM sensor alerts for low glucose (glucose <80 mg/dL).

Secondary Objectives:

- Determine the incidence of severe (glucose <40 mg/dL), moderate (glucose between 40 and 55 mg/dL), or mild (glucose between 56 and 70 mg/dL) hypoglycemia (cases of hypoglycemia/number of patients x 100) during ICU admission and the incidence rates (cases of hypoglycemia/1000 patients x hour) in critically ill patients undergoing insulin treatment using CGM sensors.
- Determine the percentage of false potential hypoglycemia alerts, defined as alerts for potential hypoglycemia that do not correspond to low capillary glucose values (glucose <90 mg/dL).
- Describe the type of patients in the ICU who are fitted with a CGM sensor in our unit.
- Describe the glycemic profile of critically ill patients undergoing insulin treatment: (Maximum glucose, minimum glucose, average glucose, glycemic variability, time in range, Hb A1c, diet used, insulin requirement, insulin protocol employed).
- Describe the actions taken by healthcare personnel following a potential hypoglycemia alarm (administration of intravenous glucose (IV) glucosmon 50% in ml, administration of IV glucose glucosmon 33% in ml, initiation of IV glucose infusion at 5% ml/h, IV glucose infusion at 10% (ml/h), among others).
- Describe the theoretical cumulative incidence of potential hypoglycemia with alternative thresholds of 70, 75, 85, or 90 mg/dL.

Materials and Methods:

Design: This is a single-center, observational, descriptive, longitudinal, and prospective study.

Setting and Study Population: The study will be conducted on patients admitted to the Intensive Care Unit (ICU) of Hospital HLA Moncloa over a period of four years.

Inclusion Criteria:

- Patients admitted to the ICU, undergoing insulin treatment, and with a placed Continuous Glucose Monitoring (CGM) sensor.
- Adults aged 18 and above.
- Patients who provide voluntary consent to participate in the study (Annex 2). If the participant is not in full physical or intellectual capacity to provide their signature on the informed consent, the investigator in charge will request consent from their direct family member or the person legally designated to make decisions on their behalf in health matters. This measure is taken to ensure the participant's rights are respected and to maintain the integrity of the consent process, even in situations where their decision-making capacity may be compromised.

Exclusion Criteria:

- Patients from whom information about CGM cannot be obtained due to technical reasons.

Sample Size:

It is expected that around 20% of patients admitted to the ICU may develop potential hypoglycemia during their stay. Based on this, it will be necessary to include 246 patients to estimate the cumulative incidence with a precision error of 5% and a confidence level of 95%. It is estimated that approximately 60 patients per year (5 patients/month) will meet the inclusion criteria, so the study is planned to last for 4 years. Annual interim analyses will be conducted, describing the cumulative incidence and incidence rate (along with their respective confidence intervals to assess the precision error of interim estimates) for the total number of patients included up to that point.

Procedures:

1. All patients admitted to the ICU and eligible for the study will be informed about it, and their informed consent will be obtained.
2. If they agree to participate, they will ensure compliance with the inclusion criteria. Therefore, they must have a continuous glucose monitoring (CGM) sensor placed according to the detailed instructions in ANNEX 1.
3. Patients will receive treatments according to the center's usual clinical practice and the criteria of their responsible physician based on the patient's characteristics in each case.
4. The device records glucose readings every 5 minutes, automatically storing the information.
5. If the device detects potential hypoglycemia at any time, healthcare personnel will act according to the device placement guide (ANNEX 1), detailing the procedure to follow, and if confirmed, it will be corrected based on the responsible physician's criteria.
6. At the time of discharge or patient exitus, the principal investigator will review the patient's medical history to create a pseudonymized database that includes patient study variables, treatments, ICU stay duration, and continuous glucose monitoring records. This information will be stored for 5 years on the hospital intranet server alongside other confidential information from the ICU at Hospital HLA Moncloa.

Alarms:

Alarms will be set using the Freestyle Libre 2 sensor reader in a similar manner for all patients.

- Low glucose alarm (subcutaneous glucose <80 mg/dL) After the alarm is triggered, capillary, arterial, or venous glucose will be checked, and actions will be taken according to the standard protocol of the ICU at Hospital HLA Moncloa.

Definitions of Hypoglycemia:

1. Potential Hypoglycemia:

- Definition: Any subcutaneous continuous glucose measurement below 80 mg/dL, confirmed by checking capillary, arterial, or venous blood glucose values up to 90 mg/dL (a margin of 10 mg/dL difference between subcutaneous glucose and blood glucose will be allowed to confirm hypoglycemia).
2. Severe Hypoglycemia:
 - Definition: Any glucose measurement below 40 mg/dL, whether in capillary, arterial, or venous blood.
 3. Moderate Hypoglycemia:
 - Definition: Any glucose measurement between 40 and 54 mg/dL, whether in capillary, arterial, or venous blood.
 4. Mild Hypoglycemia:
 - Definition: Any glucose measurement between 55 and 69 mg/dL, whether in capillary, arterial, or venous blood.
 5. False Hypoglycemia:
 - Definition: Any subcutaneous continuous glucose measurement below 80 mg/dL that is ruled out by checking capillary, arterial, or venous blood glucose values above 90 mg/dL.

Capillary, Arterial, and Venous Glucose:

- Critically ill patients typically undergo glucose determinations multiple times throughout the day and in response to specific symptoms (dizziness, fatigue, weakness, headaches, confusion, speech alterations, blurred vision, seizures, and coma). These measurements may include capillary glucose at the bedside, arterial blood gas analysis, or laboratory-based analysis of arterial or venous blood.
- The results of all glucose determinations performed on the patient will be systematically recorded. This approach will capture the incidence and incidence rate of mild, moderate, and severe hypoglycemia occurring during the hospitalization.

Variables:

- Patient ID
- Date of ICU admission
- Date of ICU discharge
- Date of sensor placement
- Date of sensor removal
- Age
- Reason for admission:
 - Depression of consciousness level and other neurological disorders
 - Acute coronary syndrome
 - Cardiac rhythm disturbances
 - Cardiopulmonary arrest
 - Heart failure/cardiogenic shock

- Hypovolemic shock
- Sepsis/septic shock
- Shock of other etiology
- Respiratory failure
- Renal failure and metabolic disorders
- Intoxications
- Head trauma
- Other traumas without traumatic brain injury
- Monitoring and postoperative surveillance
- Monitoring and surveillance of non-surgical procedures
- Other unspecified medical or surgical diseases
- Type of admission:
 - Urgent
 - Scheduled
 - Unknown
- Type of patient:
 - Medical
 - Surgical
 - Unknown
- Origin:
 - Operating room
 - Emergency
 - Conventional hospitalization
 - Other areas of the hospital
 - Another hospital
- Status at ICU discharge:
 - Alive
 - Lethal exitus
- Hypertension (yes/no)
- Diabetes Mellitus (yes/no)
- Dyslipidemia (yes/no)
- Current smoker (yes/no)
- Current ex-smoker (yes/no)
- Hb A1c at admission
- SAPS3 at admission
- Number of potential hypoglycemic events
- Number of severe hypoglycemic events
- Number of moderate hypoglycemic events
- Number of mild hypoglycemic events
- Number of false hypoglycemic events
- Continuous subcutaneous glucose values (recorded every 5 minutes)
- Maximum glucose (median \pm IQR or mean \pm SD)
- Minimum glucose
- Average glucose
- Glycemic variability
- Time in range
- Diet used

- Insulin requirement
- Action taken for hypoglycemia:
 - Administration of intravenous glucose (IV) glucosmon 50% in ml
 - Administration of IV glucose glucosmon 33% in ml
 - Initiation of IV glucose infusion at 5% ml/h
 - IV glucose infusion at 10% (ml/h)
 - Other
- Insulin protocol used:
 - Modified from Brown et al. (ANNEX 3)
 - Other

Statistical Analysis Plan

To describe the sociodemographic and clinical characteristics, as well as the glycemic profile of patients, qualitative variables will be summarized using absolute and relative frequency (n and %). For quantitative variables, the normality will be assessed (using Shapiro-Wilk tests), and mean \pm standard deviation (SD) or median and interquartile range [Q1, Q3] will be calculated to summarize the data.

The cumulative incidence (risk) and the incidence rate of potential hypoglycemia (defined by the continuous glucose monitoring system as <80 mg/dl) during the ICU stay will be calculated. Additionally, the cumulative incidence or incidence rate of mild, moderate, and severe hypoglycemias will be determined. For each of these epidemiological measures, a 95% confidence interval (CI) will also be calculated. The proportion of false hypoglycemias and the proportion of hypoglycemias overlooked by the continuous glucose measurement system, along with their corresponding 95% CIs, will be determined. The cumulative incidence and incidence rate of potential hypoglycemias will also be calculated using alternative thresholds (70, 75, 85, or 90 mg/dL). Statistical analyses will be performed using the STATA BE v.14 software (StataCorp) with a significance level of 5%.

Limitations

This is a single-center study, and other units may have different protocols for surveillance, target glucose range, prevention, or treatment of hypoglycemias, or admit patients with baseline characteristics different from those in this sample. Therefore, the conclusions of this study may not be applicable to other units.

Ethical and Legal Aspects

This study will be conducted in accordance with the current legislation. Both researchers and healthcare personnel at HLA Moncloa University Hospital will adhere to strict confidentiality in accessing, collecting, and processing data in the databases, while also committing to strict compliance with relevant legislation: Law 41/2002, of November 14, regulating the autonomy of the patient and the rights and obligations regarding clinical information and documentation; Organic Law 3/2018, on personal data protection and guarantee of digital rights; and Regulation (EU) 2016/679 of the European Parliament and of the Council of April 27, 2016,

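### The primary endpoint, potential hypoglycemia, is a sensor reading below 80 mg/dL in the objective and analysis section but needs blood confirmation in the definitions list; the false-alert rule also differs

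*Protocol*

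**What the plan says.** The protocol describes the primary event in several places.

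- **Study aim** (end of the introduction): "potential hypoglycemic events (defined as subcutaneous glucose <80 mg/dL detected by CGM".
- **Primary Objective**: "Potential hypoglycemia will be considered when the CGM sensor alerts for low glucose (glucose <80 mg/dL".
- **Statistical Analysis Plan section**: "potential hypoglycemia (defined by the continuous glucose monitoring system as <80 mg/dl) during the ICU stay will be calculated".
- **Definitions of Hypoglycemia, item 1**: "Any subcutaneous continuous glucose measurement below 80 mg/dL, confirmed by checking capillary, arterial, or venous blood glucose values up to 90 mg/dL". A parenthesis there explains the 10 mg/dL margin as the tolerance for confirming the event.

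Two further places use the term without defining it. The Hypothesis expects measures to verify the event in every patient who has potential hypoglycemia. Procedures, step 5, has the device detect potential hypoglycemia first, with confirmation following.

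False alerts are also described twice. The Secondary Objectives judge an alert against capillary glucose and treat a value as low if it is under 90 mg/dL. Item 5 of the definitions accepts any of the three blood sources and calls the event false if the value is above 90 mg/dL.

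The Variables list has a field "Number of potential hypoglycemic events" and another for false events, but no field for the number of alerts.

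**The concern.** This is a descriptive study, so the primary risk and rate are its main result, and both are also to be reported at each annual interim analysis. Two analysts working from different sections of the same protocol would count different events. Whoever fills in the field for potential events faces the same choice. Under the objective, false events are a subset of potential events; under Definitions 1 and 5 the two exclude each other. If the choice is left until data are in hand, the definition could be picked after the results are known.

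**Working it through.** **1. How each text classifies an alert (sensor below 80 mg/dL)**

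| Blood check after the alert | Primary event: aim, objective, analysis section | Primary event: Definition 1 | False: Definition 5 | False: Secondary Objective |
|---|---|---|---|---|
| Capillary value below 90 | yes | yes | no | no |
| Capillary value exactly 90 | yes | yes | no | yes |
| Capillary value above 90 | yes | no | yes | yes |
| Only an arterial or venous value, above 90 | yes | no | yes | no capillary value to judge by |
| No blood check | yes | no | no | no capillary value to judge by |

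The two primary definitions disagree in the last three rows. The two false-alert rules disagree at exactly 90, and the capillary-only rule does not cover the last two rows.

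**2. Effect on the rate**

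Let A be all alerts, C those confirmed, F those refuted and U those not checked, so A = C + F + U. The sensor-only numerator is A and the Definition 1 numerator is C. They differ by F + U. The difference equals the false-alert share only if U = 0.

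**3. The plan's own figure**

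Inputs from Sample Size: expected risk p = 0.20, precision d = 0.05, confidence 95%.

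n = 1.96² × p(1 − p) / d² = 1.96² × 0.20 × 0.80 / 0.05² = 245.9, rounded up to 246. The stated number reproduces.

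**4. Effect on the risk (illustration)**

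Assume that 20% is the alert risk, and let g be the share of alerted patients with no confirmed alert. The documents give no value for g, so a range is shown. Confirmed risk = 20% × (1 − g).

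| g | Confirmed risk | Shift |
|---|---|---|
| 10% | 18% | 2 points |
| 30% | 14% | 6 points |
| 50% | 10% | 10 points |

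The shift is 20% × g, which equals the planned 5 points at g = 25%.

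**5. Which definition fits the rest of the text**

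The aim, the objective and the analysis section define the event by the sensor alone. The Hypothesis and step 5 of Procedures place it before verification. A smaller indication comes from the planned recount, which "will also be calculated using alternative thresholds (70, 75, 85, or 90 mg/dL". The blood check is tied to the "Low glucose alarm (subcutaneous glucose <80 mg/dL", so readings from 80 to 90 mg/dL trigger no check, and a confirmed definition could not be applied uniformly at 85 or 90. This last argument carries less weight, because the objective calls that recount theoretical.

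**The case against.** The strongest reply is that the analysis section already instructs the analyst, and its rule is sensor-only. Three statements define the event that way and two more imply it, so Definition 1 looks like one misplaced clause. Sensor readings are stored every 5 minutes and all blood glucose results are recorded, so either version can be recounted. This stands. It limits the weight of the point and indicates which way to resolve it. It does not remove the conflict, because Definition 1 sits in the formal list of definitions and states its condition explicitly.

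A reader might infer more than the documents support:

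- **That the primary endpoint has no governing definition.** The analysis section gives one; the definitions list contradicts it.
- **That the false-alert percentage could be taken over confirmed events.** The Secondary Objective asks for a percentage of alerts. Under Definitions 1 and 5 false and potential events exclude each other, so false over confirmed events would not be a proportion.
- **That the sample size is wrong.** It reproduces. If 20% is the alert risk, the sensor-only endpoint loses no precision.
- **That the 20% is wrongly sourced.** The Hypothesis and the introduction's severe-hypoglycemia range cite the same reference, but that reference is not at hand and may hold other figures. The Hypothesis and Sample Size both word the 20% as an expectation.

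**Conclusion.** The contradiction is real and should be fixed. The protocol gives two incompatible definitions of its primary event and two incompatible rules for a false alert. The illustrated effect is a 2 to 10 point difference in the primary risk. It rests on two assumptions: that 20% is the alert risk, and that 10% to 50% of alerted patients have no confirmed alert. The actual size is unknown until alerts and blood checks are tabulated. The exact-90 conflict touches a single glucose value; the difference in blood source is the more material half of the false-alert conflict.

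This is a defect of wording, not of design or data collection. Annex 1 was not available, nor was any separate statistical analysis plan; either may say more, but the conflict within the protocol's own text would remain.

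**What to change.** 1. Reconcile Definition 1 with the aim, the Primary Objective and the analysis section: for the primary risk and rate, count sensor glucose below 80 mg/dL whether or not blood confirms it.
2. Make the Variables field for potential events follow that definition.
3. Report blood-confirmed events as a secondary measure under a different name.
4. Use one false-alert rule in the Secondary Objectives and in Definition 5: the same blood sources, and exactly 90 mg/dL on the same side. Take alerts as the denominator and report unchecked alerts separately.
5. State which event the 20% planning figure refers to. The 246 need not change.

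These are analysis definitions only and alter no clinical action. The cost is protocol wording and one secondary tabulation from data already recorded. The change should be made before the next interim report.

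### Each grade of hypoglycemia is defined by any single blood reading in its band, so one episode sampled more than once counts as several events and can fall in several grades

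*Protocol*

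**What the plan says.** The Protocol, under Definitions of Hypoglycemia, grades hypoglycemia by individual blood values:

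- Severe: "Any glucose measurement below 40 mg/dL, whether in capillary, arterial, or venous blood".
- Moderate: "Any glucose measurement between 40 and 54 mg/dL, whether in capillary, arterial, or venous blood".
- Mild: "Any glucose measurement between 55 and 69 mg/dL, whether in capillary, arterial, or venous blood".

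The section on capillary, arterial and venous glucose gives the data source: "The results of all glucose determinations performed on the patient will be systematically recorded". It adds that this is how the incidence and the rate of the three grades will be obtained. The Variables list has one event count per grade, such as "Number of moderate hypoglycemic events". The Secondary Objectives give the incidence of each grade as "cases of hypoglycemia/number of patients x 100" and put the same kind of cases over patient-hours for the rate. The Statistical Analysis Plan section promises a 95% confidence interval for each measure without naming a method.

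On sampling, the Protocol says "Critically ill patients typically undergo glucose determinations multiple times throughout the day and in response to specific symptoms" and, under Alarms, "After the alarm is triggered, capillary, arterial, or venous glucose will be checked".

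None of these sections gives a start or end of an episode, a minimum separation between events, or a rule that grades an episode by its lowest value. None says that cases means patients.

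**The concern.** A low glucose is an episode with a course. If it is sampled more than once, the readings can fall in the same band or in different bands. A definition met by any one reading turns each of them into a qualifying event, so the count depends partly on how often blood is drawn. There are two separate effects:

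- **Same-band repeats.** Two readings in one band during one episode give two events of that grade. This raises event counts and rates, including the severe rate. It raises the cumulative incidence only if cases are counted as events and not as patients.
- **Cross-band readings.** A severe episode that is also read in the moderate and mild bands adds to all three grades. This raises the moderate and mild figures both as rates and as cumulative incidence, even when each patient is counted at most once per band.

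These are the study's only graded measures of blood-confirmed hypoglycemia. A mild incidence that includes readings from severe episodes cannot be read as the incidence of mild hypoglycemia. Comparison with other units is also confounded by differences in sampling frequency.

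**Working it through.** **1. The plan's own figure.** The only figure that can be recomputed is the sample size. Inputs from Sample Size: p = 0.20, precision d = 0.05, 95% confidence (z = 1.95996).

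n = z² × p(1 − p) / d² = 3.84146 × 0.16 / 0.0025 = 245.85, rounded up to 246. It reproduces, and it does not depend on the severity grades.

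**2. The definitions applied reading by reading.** The bands are those in Definitions of Hypoglycemia; the readings (mg/dL) are assumed.

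| One episode | As written | Graded once by lowest value |
|---|---|---|
| 38, 50, 62, 85 | 1 severe + 1 moderate + 1 mild = 3 | 1 severe |
| 48, 52, 60, 66, 80 | 2 moderate + 2 mild = 4 | 1 moderate |
| 62, 66, 75 | 2 mild = 2 | 1 mild |

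The first row is purely cross-band, the third purely same-band, and the second is both. If patients are counted once per band, the third row falls to one mild case. The first still enters all three grades.

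**3. Size of the cross-band effect.** The documents give no band-specific rates and no number of rechecks per episode, so both are assumed. Take 100 episodes, one per patient, with lowest values 10 severe, 30 moderate and 60 mild. Let f be the fraction of deeper episodes that also yield one reading in each higher band.

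- Moderate multiplier = (30 + 10f) / 30
- Mild multiplier = (60 + 30f + 10f) / 60 = (60 + 40f) / 60
- Severe stays at 10

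| f | Moderate count | Multiplier | Mild count | Multiplier | All events |
|---|---|---|---|---|---|
| 0 | 30 | 1.00 | 60 | 1.00 | 100 |
| 0.25 | 32.5 | 1.08 | 70 | 1.17 | 112.5 |
| 0.50 | 35 | 1.17 | 80 | 1.33 | 125 |
| 1 | 40 | 1.33 | 100 | 1.67 | 150 |

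With one episode per patient, the multipliers apply equally to patients counted once per band. If 10% of patients had an episode (an assumption), mild cumulative incidence would go from 6% at f = 0 to 10% at f = 1, and moderate from 3% to 4%. Same-band repeats would further raise the rates.

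**4. Band limits.** Secondary Objectives uses 40 to 55 for moderate and 56 to 70 for mild; Definitions of Hypoglycemia uses 40 to 54 and 55 to 69. A reading of 55 is moderate in one place and mild in the other. A reading of 70 is mild in one and outside all grades in the other. The double counting does not depend on this, but an episode rule needs a single upper limit to close an episode.

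**The case against.** The best defence is that the definitions say which value qualifies for a grade, not how readings are added up. The Variables list refers to events, not readings. Potential hypoglycemia is worded in the same way on sensor values stored every 5 minutes, yet the primary objective ties it to the sensor alert, so the wording need not mean one event per reading. Grouping could then be left to an analysis plan that is not shown.

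This does not remove the point. For the blood-based grades, nothing plays the part of the alert: the Protocol goes directly from all determinations to incidence and rate. Counting each patient once per band is a fair reading for cumulative incidence and removes same-band repeats there, but not the cross-band overlap. Overlapping grades could be a deliberate choice, but the Protocol does not say so.

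Other parts of the defence stand, and they limit what may be inferred:

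- A reader might infer that blood is sampled more often once a low value is found. The text describes routine, symptom-driven and alarm-driven checks, but not rechecking during recovery. The annexes are not shown, so this remains an assumption.
- A reader might take increases of 33% and 67% as expected or minimum values. They are the f = 1 case of an invented mix; at f = 0 there is no cross-band inflation.
- A reader might conclude that the planned intervals are too narrow because a simple Poisson method assumes independent events. No interval method is named, so this cannot be charged to the plan.

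**Conclusion.** The point holds. The stated definitions, applied to all recorded readings without an episode or lowest-value rule, count one repeatedly sampled episode as several events. Same-band repeats affect event counts and rates; cross-band readings affect moderate and mild in both rate and cumulative incidence. Severe is open to same-band repeats only.

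The actual size cannot be derived. Under the assumed 10/30/60 mix, the cross-band multiplier runs from 1.00 to 1.33 for moderate and from 1.00 to 1.67 for mild as the resampled fraction goes from 0% to 100%. The range would change with a different mix. These are descriptive secondary outcomes, so the correction should be made, but it does not touch the primary sensor-based outcome or the 246 patients.

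**What to change.** 1. Reconcile the band limits between Secondary Objectives and Definitions of Hypoglycemia, so that one set is used throughout.
2. Define the analysis event as an episode: consecutive blood values in the hypoglycemic range, closed by a value above it or by a prespecified maximum time gap. Without the gap, two lows many hours apart with no reading between them would merge, and the count would again depend on sampling.
3. Assign each episode once, to the band of its lowest value.
4. Use episodes as the numerator of the rates. For cumulative incidence, use patients with at least one episode of that grade. Worst grade per patient may be added, but should not replace this, because it would drop from the mild risk a patient who had separate mild and severe episodes.
5. Because a patient can have several episodes, use patient-clustered (robust or bootstrap) variance for the rate intervals.
6. Extract each blood value with its time. The Variables list names counts per grade but no individual blood values or times; if only the counts reach the database, episodes cannot be rebuilt from it. The rule should therefore be fixed before extraction.

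The cost is a few sentences of definition, a little more extraction of values that the Protocol already says are recorded, and some programming. Reported mild and moderate counts may be lower than under the present wording. The sample size does not change.
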